9.7. Vital Signs and Physical Evaluations

Toxicity grade criteria for vital signs can be found in [Table 3](#). Unplanned vital signs measurements will be listed, but excluded from tabular and graphical summaries, except when calculating the maximum severity post-baseline.

Vital signs results will be listed ([Listing 15](#)).

Vital signs results will be summarized in tables and figures:

- Tabularly, by parameter, treatment, time point, and toxicity grade (including maximum severity post-baseline) ([Table 25](#))
- Tabularly, by summary statistics for change from baseline, reported by parameter, treatment, and time point ([Table 26](#))
- Graphically, using box plots showing the change from baseline by parameter, treatment, and time point ([Figure 39](#), [Figure 40](#), [Figure 41](#), [Figure 42](#), [Figure 43](#))

The following parameters will be presented (in order): Systolic Blood Pressure, Diastolic Blood Pressure, Heart Rate, Respiratory Rate, and Temperature

Vital signs parameters that have grading criteria for both decreases (result lower than normal range and baseline measurement) and increases (result higher than normal range and baseline measurement) will be summarized separately by direction of change.

In tables summarizing toxicity grading, maximum severity observed for the parameter after dosing and within the same period will be summarized (max severity post-baseline). Results of maximum severity for “Any Parameter” will be included. For “Any Parameter” results, the maximum severity across all vital signs parameters is summarized by time point, and from maximum severity post baseline.

The study protocol allows measurements of vital signs to be repeated in the case of an abnormal measurement. The following rules will be used to decide which measurement to include in summaries if more than one replicate was entered into the clinical database.

- If the first replicate is normal, then it will be used for analysis
- If the first replicate is abnormal, and the second replicate is also abnormal, then the first replicate will be used if has a severity equal to or greater to the second replicate, or the second replicate will be used if the second replicate has a higher severity than the first replicate.
- If the first replicate is abnormal, the second replicate is normal, and a third replicate measurement was not performed, then the first replicate will be used in the analysis.
- If the first replicate is abnormal, the second replicate is normal, and the third replicate is normal, then the second replicate will be used in the analysis.
- If the first replicate is abnormal, the second replicate is normal, and the third replicate is abnormal, then the first replicate will be used if has a severity equal to or greater to the third replicate, or the third replicate will be used if the third replicate has a higher severity than the first replicate.

Vital signs replicates not used in the analysis will not be listed.

PE findings will be listed ([Listing 16](#)).

9.8. 12-Lead Standard ECG

Toxicity grade criteria for 12-lead standard ECG parameters (PR and QTcF intervals) can be found in [Table 3](#). 12-lead standard ECG interval measurements ([Listing 17](#)), and overall interpretation and comments ([Listing 18](#)) will be listed. Unplanned 12-lead standard ECG measurements will be listed but excluded from tabular and graphical summaries.

12-lead standard ECG results will be summarized in tables and figures:

- Tabularly, 12-lead standard ECG change in overall interpretation from baseline will be shown by treatment and time point in [Table 27](#).
- Tabularly, by parameter, treatment, time point, and toxicity grade (including maximum severity post-baseline) ([Table 28](#))
- Tabularly, by summary statistics for change from baseline, reported by parameter, treatment, and time point ([Table 29](#))

-
- Graphically, using box plots showing the change from baseline by parameter, treatment, and time point ([Figure 44](#), [Figure 45](#), [Figure 46](#), [Figure 47](#), [Figure 48](#), [Figure 49](#))

The following parameters will be presented (in order): PR Interval; QRS Duration, QT Interval; QTcF Interval, RR Interval; ECG Mean Ventricular Rate.

9.9. Concomitant Medications

All medications will be coded using the current version of the WHO Drug dictionary. The use of prior and concomitant medications taken during the study will be summarized by Anatomical Therapeutic Code ATC 1 and ATC 2 (separately in [Table 30](#) for prior medications and [Table 31](#) for concomitant medications). Individual subject listings will be presented for all prior and concomitant medications (separately in [Listing 19](#) for prior medications and [Listing 20](#) for concomitant medications).

9.10. Tolerability

Tolerability to zoliflodacin (see Section 3.3) will be summarized for all subjects in the safety population who have received a dose of zoliflodacin ([Table 32](#)). Each subcomponent of tolerability will be included in the summaries: 1) subject discontinued study drug due to an AE, 2) subject choose to withdraw from the study due to an AE at any time from first dose of zoliflodacin until end of study, or 3) subject was withdrawn from the study by the investigator due to an adverse event at any time from first dose of zoliflodacin until end of study.

10. PHARMACOKINETICS

The PK Analysis Population and PK Analysis Subset are defined in Section 6.3. If there are subjects who do not have sufficient samples for a complete analysis, a modified analysis will be conducted in which some or all PK parameters may not be estimated for those subjects, but available PK concentrations will still be tabulated and graphed.

Summaries of PK data across subjects will be performed using the PK Analysis Subset by treatment (dose of zoliflodacin). Zoliflodacin concentrations will be reported in units of ng/mL. Moxifloxacin concentrations will not be measured in this study.

The below describes the basic tabular and graphical summaries of zoliflodacin PK data as well as the noncompartmental analysis (NCA). Analysis of zoliflodacin concentration and exposure data in the context of Holter ECG results is discussed in the ECG SAP.

10.1. Missing Data and Imputations

Analyte concentrations identified as laboratory errors will be indicated as such in the report and may be excluded from analyses. Time points below the lower limit of quantification (LLOQ; 1.00 ng/mL), referred to as below quantification limit (BQL), preceding the first PK concentration above the LLOQ will be imputed as 0 for plotting and for all calculations including NCA and summary statistics. All other BQL values will be missing for analysis purposes.

If the exact time of sample collection for PK is not recorded, the collection time will be imputed as the planned time for analysis. If the exact time is not known, but it is known that the sample was collected outside of the protocol defined time window for collection, then the time point may be excluded from analysis at the discretion of the PK analyst. Rationale for excluding results from analysis will be described in the CSR.

Collection of plasma samples outside of the protocol defined time window for the time point will not result in exclusion of the sample result from NCA or, typically, exclusion from calculation of summary statistics for the respective time point. PK samples collected out of window will be evaluated on a case to case basis and in extreme cases may be excluded from concentration summary statistics and plots of mean concentration. Exclusion of time points, including the justification, will be stated clearly in the report.

Missing data due to non-collection of samples will not be imputed. A geometric mean (GM) of concentrations will be treated as missing for sets of data points containing a BQL value.

10.2. Tabular and Graphical Summaries of Zoliflodacin Concentration-Time Profiles

Zoliflodacin concentrations in plasma will be listed by subject and dosing period with separate columns for concentrations reported by the lab and concentrations used for analysis ([Listing 27](#)). The listings will indicate both the nominal time, and actual time associated with the sample. All times will be in units of h.

Zoliflodacin concentrations in plasma will be summarized by dose and time point ([Table 33](#), [Table 34](#)) and plotted.

- Individual profiles by zoliflodacin dose as linear plots ([Figure 50](#), [Figure 51](#), [Figure 52](#), [Figure 53](#), [Figure 54](#), [Figure 55](#), [Figure 56](#), [Figure 57](#))
- Individual profiles by zoliflodacin dose as semi-logarithmic plots ([Figure 58](#), [Figure 59](#), [Figure 60](#), [Figure 61](#), [Figure 62](#), [Figure 63](#), [Figure 64](#), [Figure 65](#))
- [Figure 66](#) will plot GM concentration-time profiles by zoliflodacin dose as linear plots.

- [Figure 67](#) will plot GM concentration-time profiles by zoliflodacin dose as semi-logarithmic plots.

10.3. Definition and Estimation of Individual NCA PK Parameters

PK parameters will be estimated through a NCA using Phoenix[®] WinNonlin[®] version 8.0 or later (Pharsight Corporation, Cary, NC). Actual post-dose time will be used for the estimation of PK parameters instead of nominal time. Individual PK parameter estimates will be listed ([Listing 28](#)).

Phoenix WinNonlin[®] NCA will use the following settings to compute parameters from plasma PK data:

- Linear Up Log Down calculation method
- Uniform weighting
- Oral dosing
- Lambda Z Acceptance Criteria
 - $R_{sq_adjusted} \geq 0.80$
 - $Span \geq 2.5$ half-lives
 - Includes at least 3 timepoints after T_{max}

C_{max}

C_{max} is defined as the maximum observed drug concentration observed in plasma over all PK sample concentrations. It will be obtained from the **C_{max}** parameter calculated by WinNonlin[®]. If there is no measurable concentration in the subject's PK profile, then C_{max} will be missing for that subject. C_{max} will be reported in units of ng/mL.

T_{max}

Time of maximum plasma concentration (T_{max}) is defined as the time at which the C_{max} occurs. It will be obtained from the **T_{max}** parameter calculated by WinNonlin[®]. If there is no measurable C_{max} in the subject's PK profile, then T_{max} will be missing for that subject. T_{max} will be reported in units of h.

K_e

The terminal phase elimination rate constant (K_e) is defined as the first-order rate constant describing the rate of decrease of drug concentration in the terminal phase (defined as the terminal region of the PK curve where drug concentration follows first-order elimination kinetics). K_e will be computed as the slope of a terminal region consisting of ≥ 3 successive points in the plot of log-transformed concentration data versus time. K_e will be estimated using uniform weighting.

Time points used in the estimation of K_e will be initially selected using the WinNonlin[®] automatic algorithm. Manually chosen time points may be used at the discretion of the PK analyst after examination of the automatically chosen points in the context of the semi-log profile. The set of points chosen must contain only timepoints after T_{max} , include at least 3 timepoints, and satisfy the Lambda Z Acceptance Criteria described above. Otherwise, the elimination rate constant and all derived parameters (apparent terminal elimination half-life [$t_{1/2}$], AUC Extrapolated to Infinity [$AUC_{(0-inf)}$], Apparent Oral Clearance [CL/F], and Apparent Volume of Distribution During Terminal Phase [V_z/F]) will be treated as missing.

The range of concentrations used to estimate K_e for each profile will be inspected by the PK analyst, who may adjust the set of concentrations used to estimate K_e if deemed necessary, but manually selected ranges must satisfy the same acceptance criteria as those chosen automatically by the WinNonlin[®] algorithm. Sets of drug

concentrations used to calculate K_e will be indicated in [Listing 27](#). This parameter will be obtained from the **Lambda_z** parameter calculated by WinNonlin[®]. K_e will be reported in units of /h.

t_{1/2}

The half-life ($t_{1/2}$) is defined as the time required for the drug concentration to decrease by a factor of one-half in the terminal phase. The $t_{1/2}$ can be estimated as $\ln(2) / K_e$. It will be obtained from the **HL_Lambda_z** parameter calculated by WinNonlin[®]. Half-life will be reported in units of h.

AUC

$AUC_{(0-last)}$ is defined as the area under the concentration-time curve from dosing (time 0) to the time of the last measured concentration. $AUC_{(0-last)}$ will be estimated using the Linear Up Log Down calculation method and obtained from the **AUClast** parameter calculated by WinNonlin[®].

$AUC_{(0-t)}$ (partial AUC) is defined as the area under the concentration-time curve from dosing (time 0) to time t . $AUC_{(0-t)}$ may be computed for one or more values of t , with specific values of t determined after observing the data. It may be determined that no partial AUCs are required for inclusion in the CSR. Specific times (t) $AUC_{(0-t)}$ will be estimated using the Linear Up Log Down calculation method.

$AUC_{(0-inf)}$ is defined as the total area under the concentration-time curve from dosing (time 0) taken to the limit as the end time becomes arbitrarily large. $AUC_{(0-inf)}$ can be calculated by adding $AUC_{(0-last)}$ to an extrapolated value equal to the last measured concentration greater than the LLOQ divided by K_e :

$$AUC_{(0-inf)} = AUC_{(0-last)} + \frac{C_{last}}{K_e},$$

where C_{last} is the last measured concentration \geq LLOQ. $AUC_{(0-inf)}$ will be obtained from the **AUCINF_obs** parameter calculated by WinNonlin[®]. If the amount extrapolated portion of $AUC_{(0-inf)}$ is $>20\%$, the estimated $AUC_{(0-inf)}$ value will be flagged when listed in the report and will be excluded from statistical summaries of parameter estimates and downstream calculations.

All AUCs will be reported in units of h*ng/mL.

CL/F

Apparent oral clearance (CL/F) can be computed as $Dose/AUC_{(0-inf)}$. It will be obtained from the **CL_F_obs** parameter calculated by WinNonlin[®]. Clearance will be reported in units of L/h.

V_z/F

Apparent volume of distribution during terminal phase (V_z/F) after non-intravenous administration can be calculated as $(CL/F) / K_e$. It will be obtained from the **Vz_obs** parameter in WinNonlin[®]. Volume will be reported in units of L.

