Appendix D: Blood Volume Withdrawn During the Trial

Table 10: Laboratory Samples and Estimated Total Blood Volume (mL)

Study Periods	Inpatient Periods 1 to 4				Outpatient Periods 1 - 4	Dosing Period 4	ET
Study Visit	Screen	Check-in	Dosing	Follow-up	Wash-out	Final	
+Study Day ^a	-21 to -2	-1	1	2	3-7	8 (±2)	
+							
HEMATOLOGY ¹	4	4		4		4	4
CHEMISTRY and serum β-HCG and FSH ¹	5	5		5		5	5
Viral Serology (HIV, HBsAg, HCV) ¹	8.5						
PK ³			54	6			6
Total volume/visit	17.5	9	54	15	0	9	15
Dosing periods multiplier	1	4	4	4		1	1
Total volume (all dosing periods)	17.5	36	216	60	0	9	15
Cumulative total volume	17.5	53.5	269.5	329.5	329.5	338.5	

^a Study Days shown correspond to days in each treatment period. For a view of the cumulative numbering of study days, please refer to [Section 7](#).

¹ Clinical blood tests (HEM, CHEM) are drawn at Screening Visit, on Day -1, and on Day 2 in each treatment period, or ET. Serum pregnancy test in all women at Screening and within 24 h before each dosing period, and at the Final Visit, or ET. FSH only at Screening in post-menopausal women.

² Viral serology tests are drawn at Screening.

³ PK serum samples are drawn on Day 1: 30 min before dosing and at 0.5, 1, 2, 3, 4, 6, 8, 12, and 24 h after dosing in each dosing period, or ET if occurs within 24 h of dosing.

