4.2. Discussion of Study Design, Including the Choice of Control Groups

The 4-period crossover design is consistent with recommendations made in the ICH E14[1] guidance. A crossover trial can be conducted since the half-life of zoliflodacin is approximately 6 h. A wash-out phase of at least 5 half-lives of the drug is generally recommended for crossover trials to minimize the risk of carryover. A washout of 3 days would be sufficient to meet the 5 half-lives criterion for both zoliflodacin and moxifloxacin, so the 8 days or more of washout specified in the protocol is expected to prevent a carryover effect of the study drug between treatments.

The 4 g dose will be used as the suprathreshold dose required by the ICH E14 Guidance for TQT studies. Exposures resulting from a 4 g dose of zoliflodacin were shown to be safe in previous studies. The 400 mg dose of moxifloxacin to be used is the highest dose recommended for use in the clinic and is commonly used as a positive control in TQT studies to ensure assay sensitivity for detecting potentially clinically significant changes in the QT/QTc interval.

Placebo and both of the 2 zoliflodacin doses will be blinded. However, moxifloxacin treatment will not be blinded. Due to the 12 sequences included in the study design, knowledge of the moxifloxacin period does not provide information about what treatments are received in the other 3 periods. Furthermore, the 12 sequences included in the study are balanced for period and first-order carryover effects.

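### The 2.5 half-life Span rule with sampling to 24 h makes Ke-derived PK parameters missing when half-life is long, biasing the half-life summary down

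*SAP*

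**What the plan says.** SAP 10.3 lists three conditions under "Lambda Z Acceptance Criteria": adjusted R-squared of at least 0.80, a Span of at least 2.5 half-lives, and a fit that "Includes at least 3 timepoints after" Tmax. The Ke paragraph adds a restriction on the window: "The set of points chosen must contain only timepoints after" Tmax. An analyst may choose the window by hand, but a hand-picked window has to meet the same conditions. If none does: "Otherwise, the elimination rate constant and all derived parameters" (half-life, AUC(0-inf), CL/F and Vz/F) are treated as missing.

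The same section has a separate safeguard for AUC(0-inf). When more than 20% of it is extrapolated, the value is flagged in the listing and "will be excluded from statistical summaries of parameter estimates and downstream calculations".

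Protocol Appendix D gives the post-dose sampling times: "at 0.5, 1, 2, 3, 4, 6, 8, 12, and 24 h after dosing in each dosing period". SAP 4.2 gives the expected half-life: "A crossover trial can be conducted since the half-life of zoliflodacin is approximately 6 h". SAP 6.5 plans no imputation, and no sensitivity summary is planned for profiles that fail Span.

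**The concern.** With the last sample fixed at 24 h, a minimum number of half-lives in the window becomes a maximum on the half-life itself. That maximum lies not far above the typical value in the plan. The profiles that fail are the slow ones, so the reported half-life describes a sample cut off at the top.

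AUC(0-inf) and CL/F are deleted with it, even where the plan's own extrapolation rule would have kept them. PK of the 2 g and 4 g doses is a secondary objective, and these parameters are summarised in SAP Tables 35 and 36, with the AUC(0-inf) ratio in Table 37.

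**Working it through.** **Inputs.** From the documents: minimum Span 2.5 half-lives, at least 3 points after Tmax, last sample 24 h (window ±2 h), half-life about 6 h, and a 20% extrapolation limit. Span is taken in its usual sense, (last time − first time)/half-life. Not in the documents: the between-subject CV of half-life (assumed 10–30%) and the start of the terminal phase, which is redacted (taken as 2 to 8 h). The plan states no figure of its own to reproduce.

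**Step 1: the ceiling.** Largest half-life that can pass = (24 − start)/2.5. Three points ending at 24 h can start no later than 8 h.
- 8 h: 16/2.5 = 6.4 h
- 6 h: 18/2.5 = 7.2 h
- 4 h: 20/2.5 = 8.0 h
- 2 h: 22/2.5 = 8.8 h

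A 6 h half-life fitted from 8 h has Span 16/6 = 2.67, only 7% above the limit. Actual times are used, so a last draw at 22 h or 26 h moves the 8 h-start ceiling to 14/2.5 = 5.6 h or 18/2.5 = 7.2 h.

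**Step 2: share lost and bias in mean half-life.** Take half-life as log-normal with median 6 h, σ = √ln(1 + CV²) and z = ln(ceiling/6)/σ. Share lost = 1 − Φ(z). Relative bias of the mean among those kept = Φ(z − σ)/Φ(z) − 1. Example, CV 20% and 6 h start: σ = 0.198, z = 0.182/0.198 = 0.921, lost 17.9%, bias 0.765/0.821 − 1 = −6.9%.

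| Start (ceiling) | CV 10% | CV 20% | CV 30% |
|---|---|---|---|
| 8 h (6.4 h) | 25.9% lost, −4.5% | 37.2%, −12.2% | 41.3%, −19.8% |
| 6 h (7.2 h) | 3.4%, −0.8% | 17.9%, −6.9% | 26.7%, −14.2% |
| 4 h (8.0 h) | 0.2%, −0.1% | 7.3%, −3.4% | 16.4%, −9.9% |
| 2 h (8.8 h) | 0.0%, 0.0% | 2.7%, −1.5% | 9.6%, −6.6% |

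**Step 3: AUC(0-inf) and CL/F.** A simulated noncompartmental analysis used a one-compartment oral model, the protocol sampling times, 10% residual error, linear-up/log-down AUC and the SAP's criteria. All half-life variation came from clearance.
- CV 20%, automatic window: 25.5% missing, half-life −8.2%, AUC(0-inf) −7.5%, CL/F +8.1%. With the analyst allowed to re-select a passing window: 12.5%, −4.8%, −4.4%, +4.6%.
- CV 30%, automatic window: 31.6%, −13.8%, −13.1%, +15.1%. With re-selection: 19.7%, −9.7%, −9.3%, +10.2%.

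At CV 30% with an automatic window, if half the variance comes from volume, the biases are −6.8% for AUC(0-inf) and +7.3% for CL/F. If all of it does, they are −0.3% and +0.3%, while the half-life bias is −14.2%.

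**Step 4: against the 20% rule.** For mono-exponential decline the extrapolated share at 24 h is roughly 2^(−24/half-life): 7.4% at 6.4 h, 12.5% at 8.0 h and 15.1% at 8.8 h. It reaches 20% at 24/log₂5 = 10.3 h. Span therefore deletes AUC(0-inf) values between its own ceiling and about 10.3 h that the extrapolation rule accepts. At CV 30% only 1 − Φ(ln(10.34/6)/0.294) = 3.2% of profiles lie above that point, against 16.4–41.3% above the 4 h to 8 h ceilings.

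**The case against.** The size is not established by the documents. The 8 h start is the latest a three-point fit allows, the automatic algorithm may start earlier, and the analyst may move the window. At CV 10% with a start at 6 h or earlier, loss is under 4%. This stands: the loss could be a few percent. Moving the window earlier has its own cost, since it may take in points before the terminal phase.

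A minimum span is also a legitimate guard against unstable slopes, and the loss would be visible, because Tables 35–37 report N for each parameter and Listings 27 and 28 show the fits. Both points are fair. But N alone does not tell a reader that the missing values are the long ones.

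A reader might go further and infer that slow eliminators vanish from the exposure results. They do not. Only the Ke-derived parameters of one profile (one subject at one dose) are lost; concentrations, Cmax, Tmax and AUC(0-last) stay. At an 8 h half-life AUC(0-last) still holds about 87.5% of the total. The secondary PK endpoint names Cmax and AUC up to 24 h, which these serve.

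A reader might also infer that the 4 g/2 g AUC(0-inf) ratio is biased. It needs both doses to pass, so it loses N. But SAP 10.4 summarises individual ratios, in which a subject's own clearance largely cancels, and no bias has been shown.

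**Conclusion.** The point holds for the Ke-derived parameters. The rule caps the half-life that can be reported at 6.4 to 8.8 h, depending on where the window starts, against a typical value of about 6 h, and manual selection cannot override it. The downward direction for half-life follows from the rule itself, given any spread above the ceiling. The directions for AUC(0-inf) (down) and CL/F (up) are conditional on clearance contributing to half-life variation; if only volume varies, both biases are close to zero.

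The size rests on an assumed log-normal with median 6 h and on an undisclosed CV and terminal-phase start. Over CV 10–30%, mean half-life is biased by about 0 to −10% from a 4 h start, −1 to −14% from 6 h and −5 to −20% from 8 h. It would be wrong to quote the top of the 8 h range as the expected loss.

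The primary QTcF analysis and the concentration-QTcF model use neither Ke nor AUC(0-inf) and are not touched. This is worth correcting in a secondary descriptive analysis, and is no threat to the trial's main conclusion.

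**What to change.** In SAP 10.3, keep adjusted R-squared of at least 0.80 and at least 3 points after Tmax as the acceptance criteria. Make Span below 2.5 a flag in the listing, not a reason to set parameters to missing. Let the existing 20% extrapolation rule decide whether AUC(0-inf) and CL/F enter the summaries. Report the number of profiles flagged at each dose, and add a second summary restricted to Span of at least 2.5, so the strict result stays visible.

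The cost is SAP wording and one extra summary. The downside is that flagged half-lives are less precise. The change also does not remove value-dependent exclusion altogether, because the 20% rule still takes half-lives above about 10 h out of the AUC(0-inf) and CL/F summaries.
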